9.1.8 Continuous Glucose Monitoring System® (CGMS)

Glucose variability and hypoglycemia duration will be determined using CGMS (Medtronic Minimed, Northridge, CA). CGMS involves the sc placement of a glucose sensor connected by tubing to a pager-sized monitoring device that stores glucose data over a 72-hour period.

Subjects will have the sensor placed in the diabetes clinic and wear it continuously for 72 – 84 hours. Then they will drop the monitoring device off or ship it to the clinic 4 days later for analysis. Subjects will need to calibrate the sensor to their capillary BG readings 4 times daily with no interval between readings exceeding 12-hours. Data from each 72-hour period will be analyzed for mean glucose concentration, mean glucose variability (absolute value of measured glucose minus 100 mg/dL), number and duration of hyper- (>180 mg/dL) and hypo- (< 54 mg/dL) glycemic episodes, and total duration of hypoglycemia^{135,140}.

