4.1 Study Endpoints

Since our primary thesis is that GLASSIA will increase islet engraftment in the early perioperative period our primary endpoint for which the study is powered is a comparison of insulin independence rates of GLASSIA treated versus control patients at day 75 post transplant. We are fortunate to have permission to utilize data from the CIT-06 trial which will allow a large number of control patients. Since our proposed trial was directly derived from CIT-06 in terms of entry criteria, treatment regimen and post transplant monitoring except for treatment with GLASSIA and related mechanistic studies, these cohorts provide us a highly relevant comparator and allow us to enroll more GLASSIA treated patients than if a randomized trial. This increases the power of the trial making it likely that we will be able to detect differences between treated and control groups should GLASSIA exert the hypothesized benefit to engraftment.

For our primary mechanistic assessment to measure engrafted functional islet mass we will rely on the frequently sampled intravenous glucose tolerance test (FSIGT) from which an AUC for insulin secretion correlates with islet mass. Each of the 24 CIT-06 patients had this test performed at day 75. Of note, we had previously considered use of a glucose potentiated arginine stimulation test for this purpose. However, no CIT-06 patients had this test performed¹³¹⁻¹³².

Because the assessment of islet graft function is dependent on complex physiologic relationships between the graft and its recipient, no single test adequately addresses the metabolic impact of the transplant. Therefore, HbA1c and the number of episodes of severe hypoglycemia will be used as clinically relevant measures of islet graft function for secondary endpoints, and additional stimulatory tests of islet graft function utilizing MMTT, glucose, and the CPGCR will be used to assess secondary endpoints. Also, the effect of islet graft function on glycemic control (HbA1c), glycemic lability (MAGE and LI), hypoglycemia (Clarke and HYPO scores), glucose variability (CGMS®), cardiovascular impact, and renal impact will be assessed as additional secondary endpoints¹³²⁻¹³⁶. Each of these were collected in CIT-06 patients and will add to the robustness of our comparison of the metabolic outcome between GLASSIA treated and control CIT-06 subjects.

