- HbA1c comparing GLASSIA treated versus control CIT-06 subjects at 1 year and 2 years following the *first* and *last* islet transplant(s)

Glycemic Control

- The change in Clarke score from baseline in GLASSIA treated versus control CIT-06 subjects at:
 - 1 year after the first islet transplant.
 - 2 Years after the first islet transplant
- β -score comparing GLASSIA treated versus control CIT-06 subjects at 1 year and 2 years following the *first* and *last* islet transplant(s)
- Glucose variability and hypoglycemia duration derived from the CGMS comparing GLASSIA treated versus control CIT-06 subjects at 1 year and 2 years following the first and last islet transplant(s)
- Basal (fasting) and 90-min glucose and c-peptide derived from the mixed-meal tolerance test (MMTT) comparing GLASSIA treated versus control CIT-06 subjects at 1 year and 2 years following the first and last islet transplant(s)
- MAGE comparing GLASSIA treated versus control CIT-06 subjects at 1 year and 2 years following the first and last islet transplant(s)
- Glycemic lability index (LI) comparing GLASSIA treated versus CIT-06 control subjects at 1 year and 2 years following the first and last islet transplant(s)
- Ryan hypoglycemia severity (HYPO) Score comparing GLASSIA treated versus control CIT-06 subjects at 1 year and 2 years following the first and last islet transplant(s)
- C-peptide: (glucose· creatinine) ratio (CPGCR) comparing GLASSIA treated versus control CIT-06 subjects at 1 year and 2 years following the first and last islet transplant(s)
- Rate of favorable outcome at each center preparing islets (rate of subjects with HbA1c \leq 6.5% and absence of severe hypoglycemic events from Day 28 to Day 730, or reduction in HbA1c of 1 point and absence of severe hypoglycemia from Day 28 to Day 730).

Repeat Transplants

- The proportion of subjects receiving a second islet transplant comparing GLASSIA treated versus control CIT-06 subjects at 1 year and 2 years following the first and last islet transplant(s)
- The proportion of subjects receiving a third islet transplant comparing GLASSIA treated versus control CIT-06 subjects at 1 year and 2 years following the first and last islet transplant(s)

Other Efficacy Endpoints

- Cardiovascular events [death, cerebrovascular accident (CVA), myocardial infarction (MI)] and changes in atherogenic profile for GLASSIA treated versus control subjects at 1 year and 2 years following the first and last islet transplant(s)

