5.4.5 Insulin Therapy

Glucose levels will be targeted to 80-120 mg/dL. Insulin (e.g., Regular®, Lispro®, NPH®, or Glargine®) will be administered as needed to maintain glucose levels in the target range. The subject will test BG five times per day (AM fasting, before lunch, 2 hours after lunch, before supper, and at bedtime). The subject's daily BG levels will be reviewed by a study nurse and/or one of the investigators three times per week during the first two weeks after discharge, and then weekly during the next month. Exogenous insulin will be withdrawn or adjusted as needed. Subjects will be considered insulin independent according to the definition of insulin independence.

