9.1.3 Glycemic Lability

Glycemic lability will be assessed by both the MAGE¹³⁴ and the LI¹²⁹.

The MAGE requires 14 – 16 capillary BG measurements over two consecutive days taken before and 2 hours after breakfast, lunch, and dinner, and at bedtime with an optional measurement at 3 AM. A glycemic excursion is calculated as the absolute difference in peak and subsequent nadir (or vice versa) glucose values, with the direction (peak to nadir versus nadir to peak) determined by the first quantifiable excursion in the two day period. All excursions > 1 S.D. of the 7 – 8 glucose readings for the day in which they occurred qualify for the analysis, where they are summed and divided by the number of qualified excursions to give the MAGE in mg/dL glucose. A MAGE > 200 mg/dL is indicative of marked glycemic lability.

The LI requires 4 or more daily capillary BG measurements over a 4 week period and is calculated as the sum of all the squared differences in consecutive glucose readings divided by the hours apart the readings were determined (range 1 to 12 hours) in (mmol/L²/hr·wk⁻¹). A LI greater than or equal to the 90th percentile (433 mmol/l²/hr·wk⁻¹) of values derived from an unselected group of T1D subjects is evidence for severe glycemic lability.

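### The CGMS glucose variability measure is a mean distance from a fixed 100 mg/dL, so it mixes glucose level with fluctuation and can report a shift in level as a change in variability

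*Combined protocol and SAP*

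**What the plan says.** Section 9.1.8 lists what will be derived from each 72-hour CGMS record. The variability item is "mean glucose variability (absolute value of measured glucose minus 100 mg/dL". I read this as the average over the record of the absolute difference between each reading and 100 mg/dL. No other definition of CGMS variability (SD, CV or similar) appears in the document.

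The same sentence makes mean glucose a separate output ("Data from each 72-hour period will be analyzed for mean glucose concentration") and adds the "number and duration of hyper- (>180 mg/dL) and hypo- (< 54 mg/dL) glycemic episodes".

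The measure feeds a named secondary endpoint in section 4.1.2, repeated in the synopsis: "Glucose variability and hypoglycemia duration derived from the CGMS comparing GLASSIA treated versus control CIT-06 subjects", at 1 and 2 years after the first and last transplant. Section 4.1 lists "glucose variability (CGMS" as a domain of its own, beside glycemic control (HbA1c) and glycemic lability (MAGE and LI).

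**The concern.** A variability measure should be zero for a constant trace and should grow as readings spread around the subject's own level. A mean distance from a fixed value does neither in general. It rises when the whole trace moves away from 100 mg/dL, whether or not the trace fluctuates.

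This matters because the trial's hypothesis is that AAT increases engrafted islet mass. If that lowers average glucose from above 100 mg/dL, the measure will tend to fall even if swings are unchanged. Section 10.1.2 makes no multiplicity adjustment and treats favorable changes in the named secondary endpoints as support for a causal effect. A quantity that partly repeats mean glucose, but carries the label of variability, could then be read as separate corroboration.

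**Working it through.** **Inputs.** From section 9.1.8: the fixed reference of 100 mg/dL and the 72-hour record. From section 5.4.5: "Glucose levels will be targeted to 80-120 mg/dL", whose midpoint is 100. The plan gives no SD, power or precision for CGMS variability (it is not in Table 9), so there is no figure to reproduce. The trace shapes below and the 5-minute sampling are my assumptions.

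**Step 1: algebra.** Write M = mean|g − 100|. Since |g − 100| = (g − 100) + 2·max(100 − g, 0),

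M = (mean glucose − 100) + 2 × (average shortfall below 100).

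If no reading is below 100, the second term is zero and M = mean glucose − 100 exactly, so fluctuation drops out. Readings below 100 do add to M.

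**Step 2: example traces.** For a sine wave of amplitude A, SD = A/√2. If it is centred on 100, M = 2A/π. For 100±50: M = 2 × 50/π = 31.8 and SD = 50/√2 = 35.4.

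| Trace (mg/dL) | M | SD | CV |
|---|---|---|---|
| Flat 180 | 80.0 | 0 | 0% |
| Flat 160 | 60.0 | 0 | 0% |
| 160±20 | 60.0 | 14.1 | 8.8% |
| 160±60 | 60.0 | 42.4 | 26.5% |
| 150±20 | 50.0 | 14.1 | 9.4% |
| Flat 140 | 40.0 | 0 | 0% |
| Flat 60 | 40.0 | 0 | 0% |
| 100±60 | 38.2 | 42.4 | 42.4% |
| 100±50 | 31.8 | 35.4 | 35.4% |

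- Flat 180, 150±20 and 100±50 score 80, 50 and 31.8. Their SDs run the other way: 0, 14.1 and 35.4.
- Flat 160, 160±20 and 160±60 all score 60, with SDs from 0 to 42.4.
- Flat 140 scores higher than a trace swinging between 40 and 160 (40 against 38.2).
- For traces centred on 100, M does follow dispersion: 31.8/35.4 and 38.2/42.4 are both 0.90.

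**Step 3: how far level dominates.** I simulated 4,000 subjects per scenario, with 864 lognormal readings each (72 h × 12 per hour), CV uniform on 10–40%, and subject mean drawn independently of CV. All of these are assumptions.

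| Range of subject means (mg/dL) | Correlation of M with mean glucose | Correlation of M with CV |
|---|---|---|
| 100–200 | 0.99 | 0.11 |
| 110–180 | 0.98 | 0.17 |
| 90–150 | 0.87 | 0.42 |

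The influence of level weakens as subjects come closer to 100 mg/dL, but it remains the larger of the two in all three scenarios.

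**The case against.** A reader might go further and infer that the measure simply captures high glucose, or that the trial cannot answer the question of fluctuation at all. The documents do not support either statement.

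- The measure is two-sided. Readings below 100 mg/dL raise it, and flat 60 scores 40. Because 100 is the midpoint of the target range in section 5.4.5, subjects near target would get a score that behaves much like a dispersion measure.
- Section 9.1.3 specifies two other measures from capillary readings. For MAGE, "A glycemic excursion is calculated as the absolute difference in peak and subsequent nadir (or vice versa) glucose values". LI uses the "sum of all the squared differences in consecutive glucose readings divided by the hours apart the readings were determined". Both are separate secondary endpoints against CIT-06, and both respond to swings.
- Mean glucose is reported from the same CGMS record, so a careful reader could see whether a difference reflects level. It is not itself named as an endpoint in section 4.1.2, so no named CGMS endpoint is formally counted twice.
- Section 10.1.2 promises qualifiers on significant secondary findings, and section 10.1.3 lists glucose variability among endpoints summarised descriptively. No power claim or stopping rule depends on it.
- The traces are invented, and a constant 180 mg/dL for 72 hours is an extreme. They show that reversal is possible, not how often it would occur here. The sentence in section 9.1.8 also cites sources that I have not seen and that may explain the formula.

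These points limit the scope and the consequence. They do not remove the defect: a constant trace away from 100 mg/dL still scores as variable. If distance from a target was intended, the label should say so. MAGE and LI cover lability elsewhere, but they do not make this endpoint measure what its name says.

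**Conclusion.** The concern holds in a limited form. The section 9.1.8 measure combines glucose level and fluctuation. It equals mean glucose minus 100 when all readings are at or above 100 mg/dL, and it can rank a flat trace above a swinging one (80 against about 32, with SDs of 0 and 35). It does reflect dispersion when mean glucose is near 100.

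The consequence is confined to one secondary endpoint, where a GLASSIA versus CIT-06 difference in mean glucose could be reported as a difference in variability. The primary endpoint, hypoglycemia duration, MAGE and LI are unaffected.

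The algebra rests on no assumption beyond reading the formula as an average of absolute differences. The correlations depend on the simulated ranges. Whether the two cohorts will differ in mean glucose is unknown, so the misreport is a possibility and not a prediction.

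**What to change.** In section 9.1.8, define CGMS glucose variability as the within-subject SD and CV over the 72-hour record. Compare these with CIT-06 where control traces or SDs are available. Keep the present quantity only under the name 'mean absolute deviation from 100 mg/dL', and do not interpret it as variability. Carry the new definition into the synopsis and sections 4.1 and 4.1.2.

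In the GLASSIA cohort this is a recalculation from records the plan already collects, with no added procedure. The cost lies on the control side. Section 4.1 says the metabolic measures were collected in CIT-06, but the documents do not say whether CGMS traces or SDs can be obtained, or whether CIT-06 used the same formula. If traces and SDs are unavailable, report SD and CV descriptively in the GLASSIA cohort and compare only the renamed measure, after confirming that CIT-06 computed it the same way.

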9.1.9 Measures of Cardiovascular Outcomes

CARDIOVASCULAR CHANGES

Whether islet transplantation affords cardiovascular benefit will be assessed by monitoring:

- Subject mortality (all cause and cardiac related). Standardized follow-up history and physical examinations for cardiovascular disease will be conducted.
- Cardiovascular events (MI, CVA) will be recorded at this time. See Appendix 4 for definitions of cardiovascular events.
- Atherogenic profile consisting of a fasting lipid panel [triglycerides, total cholesterol, high density lipoprotein (HDL), low density lipoprotein (LDL, calculated) and non-HDL cholesterol (calculated), c-reactive protein, apolipoprotein A1 and apolipoprotein B will be assessed. Each blood sample collected for the atherogenic profile will be analyzed at each site.
- The ratio of apolipoprotein A1 and apolipoprotein B.

9.1.10 Renal Impact

Whether islet transplantation has beneficial effects on the renal allograft in IAK subjects will be assessed by monitoring:

- Loss of renal allograft survival defined as a permanent return to dialysis, retransplant, or death;
- Renal allograft function measured by SCr, eGFR, spot urine albumin creatinine ratios, and protein excretion; and
- The investigators at each site have agreed that renal biopsies may be done for clinical purposes.

9.2 Immunologic Testing

Although insulin independence can be achieved via transplantation of an adequate number of viable, functional islets, a gradual reduction in the percent insulin independent subjects occurs over time, with approximately 25% of subjects still insulin free at 4 years post-transplant.

Immune mediated islet destruction in the form of allorejection and/or recurrent autoimmunity, as well as attrition of a marginal islet mass due to exhaustion and/or toxicity of immunosuppressive agents, have all been postulated to play a role in islet loss. In order to begin to dissect the role of immune mediated reactions in allograft loss, tests will be done to determine if sensitization to donor allo or islet autoantigens has occurred. In addition, maintenance of protective immunity in the setting of immunosuppression will be addressed, as will the role of innate immune reactions in the early post-transplant period.

While methods for determination of allo and autoantibody have been extensively studied and are fairly well-established, reliable, reproducible and validated methods for assessment of T cell immunoreactivity to allo and/or autoantigens do not exist. For the most part, these techniques are time-consuming, technically demanding and require large blood volumes and significant staff time for set up and analysis of the resultant data. Several methods are undergoing testing in multiple T1D consortia (e.g., ELISPOT, tetramer staining, T cell proliferation assays) to determine which tests provide the most reliable data with regards to distinguishing between subjects with T1D vs. normal controls (for autoantigen) and to improve techniques for assessing recipient anti-donor reactivity.

9.2.1 Immune Assays

HLA TYPING OF DONORS AND RECIPIENTS, CROSMATCHING

HLA typing of donors and recipients, as well as crossmatching, will be done at individual centers. A negative crossmatch is required in order for transplantation to occur.

ALLOANTIBODY

Development of alloantibody is generally associated with long term graft loss. Development of alloantibody specific for 1 or 2 HLA antigens can now be defined using assays that incorporate HLA specific monoclonal antibodies. Site will perform Luminex (single antigen bead) testing via their local laboratories.

AUTOANTIBODY

The role of autoantibody in graft loss remains unclear. [name]'s lab in Denver (Barbara Davis Center) will provide core lab service for autoantibody assessments.

MEASURES OF INNATE IMMUNITY

In order to correlate expression of proinflammatory or procoagulant markers on islets with recipient response in the early posttransplant period, ethylenediaminetetraacetic acid (EDTA) anti-coagulated blood will be collected for assessment of thrombin-antithrombin (TAT), C3a and c-peptide levels. Samples will be sent to Quest Laboratories for analysis.

ARCHIVED SERUM AND DNA

In order to ensure that we will ultimately gain as much information as possible from this trial and due to the ongoing development of assays, serum and DNA will be archived and batch shipped to [name] at Yale, for analysis.

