4.1.2 Secondary Endpoints

Key Secondary Endpoint

Insulin independence

- The proportion of GLASSIA treated versus control CIT-06 subjects who are insulin independent after 1 or more islet infusions at:
 - 1 year after the first islet infusion
 - 1 year after the last islet infusion
 - 2 years after the first islet infusion
 - 2 years after the last islet infusion

Other Secondary Endpoints

Insulin Utilization

- The proportion of GLASSIA treated versus control CIT-06 subjects who are insulin independent after 1 or more islet infusions at:
 - 1 year after the first islet infusion
 - 1 year after the last islet infusion
 - 2 years after the first islet infusion
 - 2 years after the last islet infusion
- Percent change from baseline insulin requirement comparing GLASSIA treated versus control CIT-06 subjects at Day 75, 1 year and 2 years following the first and last islet transplant(s)

Islet Mass

The relative functional engrafted islet mass comparing GLASSIA treated versus control CIT-06 subjects using FSIGT testing at:

- Day 75 after the first islet transplant
- 1 year after the first islet transplant
- 2 years after the first islet transplant
- Correlation of markers of early islet loss as assessed by the rapid release of thrombin-anti thrombin complexes (TAT), C3 and c-peptide, and insulin specific DNA with FSIGT and clinical markers of islet function (HbA1c, insulin independence rates, duration of islet function and insulin independence)
- The proportion of GLASSIA treated versus CIT-06 control subjects with both an HbA1c ≤ 6.5% AND an absence of severe hypoglycemic events:
 - From Day 28 to Day 365 after the first islet transplant
 - From Day 28 to Day 730 after the first islet transplant.
- The proportion of GLASSIA treated versus control subjects with both an HbA1c < 7.0% AND free of severe hypoglycemic events:
 - From Day 28 to Day 365 after the first islet transplant.
 - From Day 28 to Day 730 after the first islet transplant
- The proportion of GLASSIA treated versus control CIT-06 subjects A reduction in HbA1c of 1 point AND an absence of severe hypoglycemia from:
 - From Day 28 to Day 365 after the first islet transplant
 - From Day 28 to Day 730 after the first islet transplant
- Number of severe hypoglycemic events comparing GLASSIA treated versus control CIT-06

subjects at 1 year and 2 years following the *first* and *last* islet transplant(s)

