																M ¹⁵	M ¹⁸	M ²¹	M ²⁴		
Visit #	1	2	3	4	5	6	7	8	9	10	11	12	13	14	Y1	15	16	17	18	Y2	
Visit Windows (specified in days)	N/A	N/A	≤ 2	N/A	N/A			± 3			± 10	± 5	± 7							± 90	
(repeat test at each islet transplant)																					
Crossmatch (repeat test at each transplant) ¹⁴			X																		
Thyroid Function (TSH)	X	X-yrly																			
Fasting C-Pep	X		X				X	X								X	X	X	X	X	
First morning spot urine (albumin & creatinine)	X	X-q3mo							X		X				X	X			X	X	
HbA1c	X	X-q3mo							X	X	X	X	X	X	X	X	X	X	X	X	
Fasting & post- prandial c-peptide ¹⁵				X	X																
Glucose immediately post-transplant ¹⁶				X																	
EBV IgG	X																				
CMV IgG, CMV IgM		X-yrly															X			X	
CMV, EBV by PCR		X-yrly	X ¹⁷									X	X								
BKV by PCR (blood)	X	X-yrly	X ¹⁷																		
GFR (CKD-EPI calculated)	X																				
MMTT - 60 & 90 min	X										X	X	X	X	X	X	X	X	X	X	

Time points (days relative to transplant)	S C R E E N	WL ¹	BL ²	D ^{0³}	D ³	D ⁷	W ¹	W ²	W ³	W ⁴	M ² _{1/2}	M ⁶	M ⁹	M ¹²	365 post-initial Tx	Year 2				730 post-initial Tx	
																M ¹⁵	M ¹⁸	M ²¹	M ²⁴		
Visit #	1	2	3	4	5	6	7	8	9	10	11	12	13	14	Y1	15	16	17	18	Y2	
Visit Windows (specified in days)	N/A	N/A	≤ 2	N/A	N/A																± 90
c-peptide & glucose ¹⁸																					
FSIGT Test	X ²⁷										X				X					X	
CGMS		X-yrly									X				X	X	X	X	X	X	
Local Pathology Testing																					
Biopsy of Auxiliary Graft				X ²⁴												X ²⁵					
Mechanistic Assays																					
TAT, C3a, C-Pep ²² Quest (San Jan Cap)			X ²⁰	X ²⁰																	
Autoantibody ²³ Barbara Davis		X													X	X	X	X	X	X	
Serum AAT level (ITN)	X						X ¹⁹	X ¹⁹	X ¹⁹	X ¹⁹											
Beta Cell DNA ²³ (Yale)		X								X	X	X	X	X	X	X	X	X	X		

1: WL = Waiting List. Repeat assessments as indicated (i.e. yrly, q3mo), while the subject is on the WL.

2: BL = Baseline. Baseline window for patients is -2 days relative to transplant.

3: Day 0 is the day of islet transplant. This SOE applies to the 1st, 2nd, and 3rd islet transplant; restarting at Day 0 for each subsequent transplant.

4: After listing, draw sample monthly for crossmatch. Run PRA by Luminex every 3 months.

5: Abdominal ultrasound to be performed within 3 days post-transplant.

6: Cardiovascular history and physical to be conducted at BL, Y1, Y2, Y3, in addition to patient physical.

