7: Chest x-ray report and films will be accepted if taken within one month prior to screening. Baseline report and films will be accepted if taken within one year of Day 0.

8: At screening, review medications. Review changes at subsequent visits.

9: Serology includes: HBc Ab, HBs Ab, HBs Ag, HCV Ab, and HIV. Do not repeat Hep B tests if HBs Ab was previously positive.

10: Test repeated Days -1, 0, +1, +2.

11: Comprehensive Metabolic Panel includes: Na⁺, albumin, Mg²⁺, Cl⁻, K⁺, alk phosphatase, total bilirubin, CO₂, creatinine, ALT(SGPT), BUN, gamma GT, glucose, ST (SGOT), Ca²⁺, phosphorus.

12: Visit window for monthly labs is +/- 10 days.

13: Complete urine or serum pregnancy at screening. Complete serum pregnancy test within 72 hours prior to transplant. If urine tests positive at anytime, confirm by serum pregnancy.

14: Sample used for crossmatch may be obtained up to 30 days prior to the start of induction therapy, as long as there is no evidence of infections or transfusions since the time the sample was drawn. Crossmatch should be repeated for subsequent islet transplants.

15: C-peptide should be drawn fasting, and twice between 1-3 hrs post-prandial on Day 3 and Day 7 post-transplant.

16: Finger stick glucose should be drawn every hour for the first 6 hours immediately post-transplant.

17: CMV, EBV, and BKV by PCR immediately prior to the transplant. Post-transplant testing may be more frequent per standard of care.

18: MMTT can be done as necessary when determining islet graft failure.

19: Drawn daily during hospitalization and prior to each AAT dose.

20: TAT, C3a, & c-peptide: pre-induction AND pre transplant, 15, 30, 60, 120 min post-tx.

21: At screening, may use results from kidney transplant.

22: Serum frozen and batch shipped after each transplant.

23: Serum frozen and batch shipped at end of study.

24: Biopsy of auxiliary graft with subsequent transplants only

25: To be done in the event of graft failure for patients who do not receive subsequent transplants

26: Drawn and shipped in real time to Quest Diagnostics between 2nd and 3rd dose of AAT

27: A baseline FSIGT Test will be optional

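### Section 9.2.1 calls for EDTA blood for TAT, C3a and c-peptide, but Appendix 1 footnote 22 tells sites to freeze serum for the same assays

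*Combined protocol and SAP*

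**What the plan says.** The paragraph on innate immunity in Section 9.2.1 states that EDTA "anti-coagulated blood will be collected for assessment of thrombin-antithrombin (TAT), C3a and c-peptide levels", and sends the samples to Quest.

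In the Mechanistic Assays block of Appendix 1, the row for these analytes, also assigned to Quest, is labelled "TAT, C3a, C-Pep ²²". Footnote 22, which that label carries, reads "Serum frozen and batch shipped after each transplant". Footnote 20 on the same row sets the sampling times: "TAT, C3a, & c-peptide: pre-induction AND pre transplant, 15, 30, 60, 120 min post-tx".

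The secondary endpoint that uses these markers, in the synopsis and in Section 4.1.2 under Islet Mass, correlates early islet loss, assessed by the "rapid release of thrombin-anti thrombin complexes (TAT), C3 and c-peptide, and insulin specific DNA", with FSIGT and clinical markers of islet function. It names C3. Section 9.2.1, the Appendix 1 row, footnote 20 and Section 10.1.3 all name C3a.

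**The concern.** The protocol gives two specimen types for one set of tubes. Section 7 sends sites to Appendix 1 for the detail of what is done at each visit, so a coordinator working from the schedule could reasonably process these samples as serum.

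The choice matters more for TAT and C3a than for most analytes. Both are products of the reactions that the trial wants to observe in the patient, and both can also arise in a tube left to clot. The background in Section 1.1 describes a rise within the first hour after infusion as the signal of interest. A sample type that can generate the same molecules after the draw mixes that signal with handling. If sites differ in which instruction they follow, a site effect is added in a cohort of 20. The specimen type cannot be changed once a sample is frozen.

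**Working it through.** The plan states no figure on this point, so the check is a comparison of texts and one count.

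**1. Are the two instructions about the same samples?** Yes. Section 9.2.1 and the Appendix 1 row name the same three analytes and the same laboratory. Footnote 22 is not a stray reference to other material:
- In the table as extracted, it is attached to this row only. The autoantibody and beta cell DNA rows carry footnote 23, which has a different shipping time (end of study).
- The archived serum in Section 9.2.1 is described separately and goes to a different laboratory.

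**2. Can both be followed?** No. EDTA prevents clotting, and serum is what remains after clotting. Section 9.2.1 says blood, not plasma. Reading it as plasma is natural, but it is a reading. No other section reconciles the two.

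**3. What would serum do?** Clotting generates thrombin, and therefore thrombin-antithrombin complexes. Without EDTA, complement can go on activating and release C3a. This is general laboratory principle. The documents give no figure for the size of the effect, and none is assumed here. The argument does not apply to c-peptide in the same way, because c-peptide is not a product of clotting or complement activation.

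**4. Can the direction be stated?** No. Under Section 5.4.3, heparin may be given with the islets and continued afterwards. The pre-induction draw, and a pre-transplant draw taken before heparin, could therefore clot under different conditions from the four later draws. With serum, the in-tube contribution may differ before and after infusion, so it could distort the change over time as well as add noise. Differences between sites can move a pooled correlation either way.

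**5. How many samples?**
- Draws per transplant (footnote 20): 2 before infusion + 4 after (15, 30, 60, 120 min) = 6.
- First transplants (synopsis, accrual objective): 20.
- Samples: 6 × 20 = 120.

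The number affected is 120 × f, where f is the share processed as serum. The documents do not give f, so the range is 0 (all follow Section 9.2.1) through 60 (half) to 120 (all follow footnote 22). The schedule restarts at each later transplant (footnote 3), so each of those adds six more draws to the base.

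**6. Which complement analyte?**

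| Place | Analyte |
|---|---|
| Synopsis, secondary endpoint | C3 |
| Section 1.1, background | C3 |
| Section 4.1.2, secondary endpoint | C3 |
| Section 9.2.1, assay | C3a |
| Section 10.1.3, analysis | C3a |
| Appendix 1, row and footnote 20 | C3a |

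No C3 assay is scheduled. Every place that tells someone what to measure or analyse says C3a.

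**The case against.** The strongest reply is that footnote 22 is loose wording. It deals with freezing and shipping, and footnote 23 uses the same phrasing for the autoantibody and beta cell DNA rows, which suggests a stock phrase. Section 9.2.1 is the only text that tells a site how to collect these samples, and it names the anticoagulant. The protocol also defers much procedural detail to a Manual of Procedures, which is not among the documents and may specify the tube. All of this stands as a reason to doubt that serum will be frozen in practice. It does not remove the contradiction, because the footnote is an operational instruction in the schedule that sites are told to use.

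It is also fair to say that the consequence is limited. FSIGT is the primary mechanistic assessment of engrafted mass (Section 4.1). The affected endpoint is a correlation with no stated CIT-06 comparison, it draws on c-peptide and insulin-specific DNA as well, and Section 10.1.3 gives TAT and C3a descriptive statistics only. That stands in full.

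A reader might infer from the endpoint wording that the trial measures the wrong complement protein. The documents do not support that. With no C3 assay scheduled, a site following the protocol would measure C3a, so the endpoint is misnamed and the data are not at risk on this account.

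**Conclusion.** Wrong as written. Section 9.2.1 and Appendix 1 footnote 22 specify incompatible specimens for the same assays, and following the footnote would put TAT and C3a at risk of forming in the tube. Up to 120 first-transplant samples are exposed. That figure is a worst case, which assumes that every site processes every sample as serum.

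A reader might go further and conclude that 120 samples are uninterpretable, or that the correlation is bound to shrink towards zero. Neither follows: the documents do not say how sites will process the samples, and they support neither a size nor a direction for the artefact. The effect is confined to the secondary and exploratory early islet-loss markers. The primary endpoint, its power and the listed comparisons with CIT-06 do not depend on them.

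The conclusion rests on two things outside the text: that an EDTA tube does not give serum, and that clotting can generate these analytes. C3 in place of C3a in the endpoint is a separate naming error.

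**What to change.** Amend footnote 22 for the TAT, C3a and c-peptide row to an EDTA sample, in line with Section 9.2.1. Confirm with the assay laboratory that plasma is the required specimen, and then say so in both places. Require the same tube and handling at all six time points and at every site.

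Record the specimen type of each stored sample. If any prove to be serum, keep them out of the TAT and C3a analyses and report how many were excluded.

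As a wording correction, replace C3 with C3a in the endpoint in the synopsis and in Section 4.1.2.

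The cost is one footnote, a matching clarification in Section 9.2.1, two endpoint words, a query to the laboratory and a check of stored samples. No extra draw or visit is needed.
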